
WOMEN'S INTERAGENCY HIV STUDY
 
SECTION 36: MALT/GALT SUBSTUDY PROTOCOL

A. STUDY PURPOSE

The purpose of this study is to evaluate the effects of HIV infection in gut-associated lymphoid tissue (GALT) and endometrial mucosal-associated lymphoid tissue (MALT) in HIV-negative and HIV-positive women at selected stages of HIV disease progression.

Our aims are to compare endometrial, ileal and sigmoid colon tissue samples in selected WIHS participants in order to determine if:

1. The perturbations in GALT, HIV-specific immune responses, apoptosis, and collagen deposition that have been reported in HIV-positive men are also found in HIV-positive women.
2. The patterns of these alterations differ among HIV disease state groups.
3. These alterations are similarly present in endometrial tissue.
4. HIV infection will be associated with reduced numbers of CD4 memory cells, increased lymphocyte activation, apoptosis, cellular turnover, T regulatory cells and collagen deposition in both gut and endometrium; the extent of the abnormalities will be directly correlated with intracellular levels of HIV RNA.
5. The extent of immune abnormality in MALT tissues will be correlated with the extent of HIV disease progression, and with expression of cellular activation markers and level of circulating soluble biologic mediators (in a pattern consistent with inflammation).
6. It is feasible to use endometrial tissue to evaluate overall mucosal lymphoid immunity in future HIV research.

B. BACKGROUND, SIGNIFICANCE, AND PRELIMINARY STUDIES

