2. STUDY PROCEDURES

a. Pre-eligibility:

WIHS sites will be provided with lists of potentially eligible participants based on the Inclusion and Exclusion Criteria listed below. Study staff will then approach potentially eligible participants at their next regularly scheduled Core Visit. Participants who are interested will have a Pre-Eligibility Screening Interview at the end of the Core Visit. Those who appear eligible will be scheduled for a Screening Visit. (*See Appendix C: Time and Events Schedule.*)

b. Screening Visit

The Screening Visit will be scheduled as soon as possible after the WIHS Core Visit. Informed consent will be obtained at this visit. All participants will answer questions about medical history, current medications, and use of intravaginal products. Urine testing for pregnancy will be performed. Participants with a positive pregnancy test will not continue in the study. Blood will be drawn for prothrombin and partial

thromboplastin tests (PT and PTT). HIV-positive participants will have blood drawn for HIV viral load, since it is anticipated that results from the prior WIHS Core Visit will not yet be available. HIV-positive participants will also be asked to report any acute medical illnesses occurring during the study period and to avoid vaccinations during the study if this can be done without compromising their health. These measures are requested because of the potential for HIV viral load changes associated with acute medical illness and vaccination.

Participants will be instructed how to perform at-home urine testing to detect luteinizing hormone (LH). LH peaks just before ovulation, and is detectable in the urine in the early luteal phase.

Study staff will dispense Clearblue brand LH surge kits (Proctor & Gamble, Cincinnati, OH) and assist the participant in determining when to start testing. (*See Appendix D: When to Start LH Surge Testing.*) The participant will notify site staff when LH is detected in the urine, so that the Endometrial Biopsy Visit can be scheduled within 7 to 9 days, at which time the participant will be in the mid-to-late luteal phase. Participants will be encouraged to contact site staff should *any* questions or concerns arise during urine testing. Study staff may also contact participants.

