home (for example, those marginally housed or living in places where bathroom access is limited), one option is to offer hospitalization at a local research center overnight. Sites should also consider this option for participants with very difficult peripheral venous access, for whom placement of a peripherally inserted central catheter (PICC) line is necessary. Sites with access to CTSA-funded CRCs may consider applying for overnight admission visits for participants who have difficulty traveling to study visits, or who are anticipated to have difficulty with the Bowel Prep.

d. *Biopsy Visit:*

FOR SOME SITES, IT WILL NOT BE POSSIBLE TO SCHEDULE THE COLONOSCOPY AND ENDOMETRIAL BIOPSY ON THE SAME DAY. IN THAT CASE, THE ENDOMETRIAL BIOPSY SHOULD STILL BE SCHEDULED BASED ON THE LH SURGE. THE COLONOSCOPY CAN BE SCHEDULED WITHIN 7 DAYS ON EITHER SIDE OF THE ENDOMETRIAL BIOPSY.

SITES PERFORMING GYNECOLOGICAL SPECIMEN COLLECTION WITHOUT SEDATION MAY WANT TO CONSIDER OFFERING PARTICIPANTS IBUPROFEN AND/OR PARACERVICAL BLOCK.

This visit will occur 7 to 9 days after the LH surge is detected, during the mid-to-late luteal phase of the menstrual cycle, when the depth of endometrial tissue is greatest. Participants will undergo a colonoscopy and endometrial biopsy (EMB). Immediately prior to these procedures, we will conduct a brief interview to collect health history and information on medication use and recent intravaginal product use. A urine sample will be collected to rule out pregnancy. Participants with a positive pregnancy test or recent intravaginal product use will not continue in the study.

Continuing participants will be assessed by the site colonoscopist who will determine the appropriate intravenous (IV) sedation to administer. Participants will have an IV line placed by Endoscopy Nursing staff. Before sedation is administered, blood for serum progesterone will be drawn through the IV line. Serum progesterone levels will be run locally to confirm menstrual cycle phase in case the histologic dating of the endometrium is equivocal. If colonoscopy and endometrial biopsy are being performed at separate visits, serum progesterone should be drawn at the EMB visit.

For HIV-positive participants, one 5-6 ml lavender top EDTA tube should be drawn at the same time as the serum progesterone. This will be used to compare HIV viral load in plasma to that in cervical secretions.

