After venipuncture, gently invert the tube 8 to 10 times and store upright at room temperature until centrifuging. Blood should be centrifuged within 6 hours. Centrifuge at room temperature at $\leq 1300 \times g$ for 10 minutes. Aliquot at least 1.1 ml into a labeled Wheaton cryovial and refrigerate for no more than six hours before freezing at -80 for shipping.

The SF site only will also draw two 10-cc lavender top EDTA tubes for peripheral blood monocytes (PBMCs) to be shipped to the UC Davis Lab.

Sedation will be administered and blood drawn through the PICC line for those participants who required PICC placement; all peripheral and PICC lines will be

removed before the participant is discharged from the study. After sedation, the participant will be placed in a right side-lying position and a colonoscope will be passed through the large intestine and through the ileo-cecal valve. At least 8 to 10 biopsy samples each of the ileum and sigmoid colon (total 16 to 20 samples) will be obtained with cold forceps using standard techniques. In the event the colonoscopist identifies any lesions, additional biopsies of the lesion(s) will be obtained as clinically indicated, and sent for routine clinical pathology at the site.

Four to five samples will be placed in Wheaton cryovials supplied by the San Francisco site and flash frozen; four to five samples will be placed in a container of 10% formalin, and one sample will be placed in another container of 10% formalin. Sites will supply their own formalin containers. All will be shipped to San Francisco.

Endoscopy nurses are used to collecting biopsy specimens; if you give her/him the tubes, s/he will probably use a small needle to tease the tissue out of the forceps into your cryovial or container of formalin. Please collect the frozen sample first so that there is no chance of contaminating the frozen specimen with formalin. The study specimens will be used to measure inflammatory cells, cytokines and other immune markers, and collagen deposition. Routine histology will be performed on the second formalin container.

(San Francisco site only will also send fresh endometrial specimens in antibiotic medium to the [name] Lab at UC Davis.)

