All biopsy specimens should be labeled with the date of collection and the unique identifier (called the Lab ID#), which the site will assign to each participant. We are not labeling the actual specimens with the WIHS ID because we are using such small cryovials and the receiving lab here in San Francisco requested we use a system that allows all the information to be on the tube directly.

Every specimen shipping form will have both the WIHSID # and the Lab ID#. The Lab code always starts with W (for WIHS), then a number from 1-6, denoting the WIHS Site (1=Bronx; 2=Brooklyn; 3=Washington, D.C.; 4=Los Angeles; 5=San Francisco; 6=Chicago). The last number is assigned sequentially as participants are enrolled. First participant at your site =1, second =2, etc.

Each specimen will be labeled with a 5-digit alphanumeric code that contains the Lab ID# and a code for the type of specimen. The code is explained below. For example, W51-EP would be assigned for endometrium preserved in formalin for the first participant enrolled at the San Francisco WIHS site. W52-IF would be assigned for a frozen ileal specimen from the second San Francisco WIHS participant enrolled.

W= WIHS

[S]= indicates which WIHS Site nationally (will be a number from 1-6)

[N]= Unique to participant, assigned in the order in which participants at each site are enrolled. First participant = 1, second = 2, etc.

Next letter= Specimen type

S = Sigmoid colon

I = Ileum

P = Cervical sPonge (Merocel spear)

W=Cervical Wick for HIV VL (TearFlo strip)

E = Endometrium

Y = Endocervical cYtobrush (San Francisco only)

C = Cervical transformation zone

B = Blood

Last Letter= How specimen received in Lab

F = Frozen

P = Formalin (Preserved)

C = Fresh (Cells) (San Francisco only)

SPECIMENS IN ORDER OF COLLECTION	Frozen Specimens	Fresh Specimens (SAN FRANCISCO ONLY)	Specimens in Formalin
Ileal biopsy	W __ -IF	W __ -IC	W __ -IP (2 containers: one with 4-5 pieces, one with 1 piece)
Sigmoid colon biopsy	W __ SF	W __ -SC	W __ -SP (2 containers: one with 4-5 pieces, one with 1 piece)
Cervical sponge for cytokines	W __ -PF	W __ -PC	N/A
Cervical wick in lysis buffer for HIV VL (HIV + participants only)	W __ -WF	N/A	N/A
Endocervical cytobrush *	N/A	W __ -YC	N/A
Endometrial biopsy	W __ -EF	W __ -EC	W __ -EP
Cervical transformation zone biopsy	W __ -CF	W __ -CC	W __ -CP
Blood for PBMCs*	N/A	W __ -BC	N/A
Plasma for HIV VL (HIV + participants only)	W __ -BF	N/A	N/A

2. **SHIPPING SPECIMENS:**

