APPENDIX C: TIME AND EVENTS SCHEDULE

Requirement	Screening Visit	At home Phase	4 to 5 Days before Biopsy Visit	1-2 Days before Biopsy Visit	Biopsy Visit	Evening of & Day after Biopsy Visit	1 wk and 2 wks post Biopsy Visit
Consent.	X						
Urine pregnancy test.	X				X		
Blood draw for PT and PTT.	X						
Ascertainment of medical history, medication use, intravaginal product use.	X				X		
Condoms dispensed as needed.	X						
Golytely dispensed with instructions. Personal wipes dispensed.	X						
SC* and Ppt** in contact. Ppt to perform home urine testing and to refrain from use of vaginal products once LH surge detected. Biopsy Visit to be scheduled 7 to 9 days after LH surge.		X					
SC makes reminder call to Ppt: Stop all prohibited medications. SC makes arrangements for medical taxi as needed.			X				
SC makes reminder call to Ppt: Clear liquid diet to begin day before (Colonoscopy) Biopsy Visit. Begin Golytely Bowel Prep at 6 pm same day (or admit to CRC for Bowel Prep).				X			
SC available via pager to assist with adherence to Bowel Prep.				X			
Colonoscopy with biopsies, EMB performed. Serum progesterone drawn at EMB Visit.					X		
SC contacts Ppt to assess for adverse events.						X	X

*SC=Study Coordinator ** Ppt=Participant

**APPENDIX D: HOW TO USE CLEARBLUE URINE TEST KITS
TO DETECT LH SURGE**

When Luteinizing Hormone (LH) rises in the body, it causes ovulation, which occurs in the middle of the menstrual cycle. This increase is called the “LH surge.” We will schedule the Biopsy Visit for 7 to 9 days after the LH surge is detected, when the depth of the endometrial tissue is at its greatest, so it is important that participants are aware how to test properly and to call as soon as the LH surge is detected.

DETERMINE WHEN TO START TESTING

To determine when to start testing, you must first determine the length of the participant’s menstrual cycle. The length of the menstrual cycle is the number of days from the first day of bleeding to the day before bleeding begins on the next period.

Determine the usual length of the menstrual cycle over the last six months. Then, refer to the Cycle Chart below to decide on which day of the menstrual cycle to begin testing.

Cycle Length	Day to Begin Testing
21 days	Day 5
22 days	Day 5
23 days	Day 6
24 days	Day 7
25 days	Day 8
26 days	Day 9
27 days	Day 10
28 days	Day 11
29 days	Day 12
30 days	Day 13
31 days	Day 14
32 days	Day 15
33 days	Day 16

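### Aim 5 depends on circulating soluble mediators, but the protocol assigns no blood specimen to them in any group

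*Protocol*

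**What the plan says.** Section A, aim 5, relates the extent of mucosal immune abnormality to disease progression and also "with expression of cellular activation markers and level of circulating soluble biologic mediators".

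The blood collected is set out in section C.2 (Study Procedures), the specimen table in section E.1 and Appendix C:

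- Screening, all women: "Blood draw for PT and PTT".
- Screening, HIV-positive women: "HIV-positive participants will have blood drawn for HIV viral load".
- Biopsy visit, all women: a progesterone sample. "Serum progesterone levels will be run locally to confirm menstrual cycle phase".
- Biopsy visit, HIV-positive women: "For HIV-positive participants, one 5-6 ml lavender top EDTA tube should be drawn at the same time as the serum progesterone". Its purpose is given directly: "This will be used to compare HIV viral load in plasma to that in cervical secretions".
- Biopsy visit, one site: "The SF site only will also draw two 10-cc lavender top EDTA tubes", for PBMCs. This is not limited by HIV status.

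In the E.1 table, the one frozen blood item is labelled "Plasma for HIV VL (HIV + participants only)". The other blood row is the San Francisco PBMC specimen, sent fresh. Section C.2.d assigns cytokine measurement to the endocervical sponges and to the biopsy tissue.

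**The concern.** The aim names an analyte, and the collection plan provides no specimen for it. The analyte matters to the study: the background in section B.1 builds its argument on blood inflammatory mediators accompanying mucosal damage, citing bacterial lipopolysaccharide and plasma interferon-gamma.

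What is drawn, from whom and when has to be settled before the visit. An analysis plan cannot recover a biopsy-day sample that was never stored. If sites follow the protocol as written, the mediator part of aim 5 has no designated biopsy-time blood in any of the five groups. For HIV-negative women there is not even a stored plasma vial that could be put to a second use.

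**Working it through.** No power or effect size is stated for aim 5, so the check is a trace of specimens with a little arithmetic.

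**1. Specimen trace**

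| Specimen | Who | Stated use | Circulating mediators? |
|---|---|---|---|
| Screening PT/PTT | all | clotting eligibility | no |
| Screening viral load | HIV-positive | viral load | no |
| Serum progesterone | all | cycle dating, run at the site | no |
| EDTA tube, 5-6 ml | HIV-positive | plasma against cervical viral load | no |
| Two 10-cc EDTA tubes | San Francisco only | PBMCs | no |
| Endocervical sponges | all | cytokines | local, not circulating |
| Gut biopsies | all | cells, cytokines, immune markers, collagen | tissue, not circulating |

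Blood items assigned to circulating mediators: 0. Stored plasma items specified for HIV-negative women: 0. HIV-negative women do give blood at every site (clotting tests and progesterone), and at San Francisco they also give EDTA blood, but no plasma aliquot from it is described.

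**2. Whether Core Visit blood would fill the gap**

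- C.2.a has women approached at a Core Visit. C.2.b places screening soon afterwards but gives no upper limit.
- LH kits are handed out at screening, and the endometrial biopsy follows a positive test by 7 to 9 days. Blood from the recruiting Core Visit therefore precedes the endometrial biopsy by at least 7 days, with no stated maximum.
- After a failed bowel preparation, C.2.d discards the progesterone and viral-load blood, and section D allows re-enrolment in the next cycle. With eligible cycles of 21 to 35 days, that adds roughly 21 to 35 days.
- Exclusion 9 bars specified illnesses and vaccination within 14 days of the Biopsy Visit. It does not cover the period around an earlier Core Visit.

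**3. Plasma available from the existing tube**

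Inputs: tube of 5 to 6 ml and minimum viral-load aliquot of 1.1 ml (both C.2.d); plasma yield of 50% to 60% (assumption, not in the protocol).

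- Low: 5 × 0.50 = 2.5 ml; 2.5 − 1.1 = 1.4 ml left.
- High: 6 × 0.60 = 3.6 ml; 3.6 − 1.1 = 2.5 ml left.

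The protocol sets 1.1 ml as a minimum, so these figures apply only if no more than that is taken.

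**4. Limits on using that tube**

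- Viral-load handling allows 6 hours to centrifugation and a further 6 hours refrigerated, up to 6 + 6 = 12 hours before freezing. The protocol does not consider whether this suits mediator assays.
- When visits are split, progesterone is drawn at the endometrial biopsy and the colonoscopy can fall up to 7 days either side. The blood would then match the endometrium exactly but the gut only to within 7 days.

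**The case against.** The best defence is that this is a substudy of an established cohort and plainly relies on cohort data. Appendix B defines the HAART-responder groups by CD4 counts before and during treatment, and two of the HIV-positive groups by long-run viral load, yet no substudy visit draws a CD4 count. Disease progression, the other correlate in aim 5, must therefore come largely from the cohort, and the mediators might too. Nor does aim 5 promise blood from the day of biopsy.

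Much of this stands. A reader might infer that the control group has no contemporaneous mediator data at all, or that HIV-negative women give no plasma. The documents do not support either. Cohort blood is not ruled out, a later Core Visit could fall closer to the biopsy than the recruiting one, and HIV-negative women at San Francisco do give EDTA blood. The missing assignment affects every group, not only controls. A reader might also infer that Core Visit blood would weaken the correlation by some known amount. The protocol gives neither the interval nor the within-woman stability of the mediators, so no such figure can be derived.

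The defence does not supply a source. The protocol never says that cohort blood will be used for this purpose. It draws fresh plasma at the biopsy visit for the viral-load comparison, which shows that timing was considered for one analyte and not for the other. The shipping text of section E.2 was not available and is not relied on either way.

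**Conclusion.** The point holds as a gap between aim 5 and the collection plan. No blood specimen is assigned to circulating mediators in any of the five groups, and no biopsy-time plasma is stored from HIV-negative women. Whether cohort blood would serve cannot be judged, because it is not named and no maximum interval to biopsy is set.

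This does not show that the correlation is impossible or that it would be biased by a particular amount. It shows that the protocol provides no specimen for it. The specimen count needs no assumption. The spare-plasma range rests on the assumed 50% to 60% yield and on using only the minimum viral-load aliquot. The gap should be closed before further biopsy visits, since the remedy works only prospectively.

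**What to change.** In section C.2.d and the E.1 specimen table:

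- Draw the same 5-6 ml EDTA tube from every participant, whatever her HIV status, at the existing progesterone draw.
- Freeze the plasma beyond the viral-load aliquot as a second labelled vial for soluble mediators. For HIV-negative women, all of the plasma is available for this.
- Set times to centrifugation and freezing that suit the mediator assays, instead of relying on the viral-load limits.
- Record the interval from this draw to the colonoscopy for split visits.

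If Core Visit specimens are the intended source, name them in aim 5, state the allowed interval from each biopsy, and limit the claim to non-contemporaneous levels.

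Cost: one extra tube in 10 to 15 HIV-negative women at a draw already being made, and one extra cryovial per participant. Tighter processing times may also add work at the sites.

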1. GALT IN HIV DISEASE

While peripheral blood T-cell (CD3+CD4+ cell) counts are an accessible measure of immunologic status in HIV infection, they are an incomplete measure of immune function in general, and are particularly poor indicators of mucosal CD4 cell populations, which are the largest in the human body. Persistence of perturbations of mucosal lymphoid tissues after HIV infection and HAART indicate that even optimal host and treatment responses do not insure recovery of normal immunologic functions.

The recent recognition of the extent of mucosal lymphoid abnormalities after HIV infection and their persistence during HAART has led to major revisions in concepts of HIV pathogenesis. Current hypotheses of immune and viral events over the course of untreated HIV infection hold that CD4 cells from GALT are severely depleted by day 14 of HIV or Simian Immunodeficiency Infection (SIV) infection, particularly CD4+ memory T cells in the lamina propria. These changes precede peripheral CD4 cell depletion.

This persistent cellular depletion in GALT occurs in humans despite near complete recovery of CD4 T cells in peripheral blood after initiation of HAART. Long-term

nonprogressors (natural controllers) are spared the loss of mucosal T cells and the chronic expression of inflammatory response genes in gut mucosa seen in patients with a more typical HIV course. Since mucosal cells can be easily replaced by cells that traffic in from other sites, depletion of CD4 memory cells within mucosal tissues does not explain the subsequent progression of HIV disease. Chronic immunologic activation and inflammatory responses are closely linked with the long-term outcomes of HIV infection. Lymphocyte activation and changes in blood inflammatory mediators often accompany mucosal abnormalities in both untreated and treated HIV patients. Immune activation is also associated with the extent of CD4 cell recovery after HAART, as well as functional abnormalities. Since activation is not limited to HIV-specific cells, persistent activation is not driven solely by lymphocyte responses to HIV itself. However, repeated episodes of HIV-induced cellular proliferation, differentiation and death may over time lead to increased cellular activation and turnover. Persistent activation could also result from CD4-depleted gut mucosa that permit leakage of bacterial antigens into systemic circulation, a concept that is supported by a recent study by Douek, *et al.*, who found that increased blood bacterial lipopolysaccharide (LPS) levels were associated with HIV infection, increased plasma IFN- γ and frequency of CD38+ HLADR+ CD8 T cells. However, HAART treatment is associated with improvements in systemic immune activation even though mucosal lymphocyte populations remain depleted. Because immune activation is to some extent responsive to HAART, viral replication thus appears to contribute directly to persistent activation, perhaps via stimulation of bystander cells by HIV-triggered responders. Immune activation plays a vital role in maintaining viral replication in mucosal tissues by providing newly susceptible cells, while direct and indirect viral effects result in depletion of susceptible substrate. Pro-inflammatory products of activated cells within the mucosa likely cause injury and apoptosis within the mucosal epithelium.

